4.2.2 Principal Secondary Outcome

Change in generic HRQOL from baseline to 12, 26 and 52 weeks as assessed using the EuroQol (EQ) 5D-5LTM and EQ Visual Analogue Score (VAS) (Appendix B-2). This short self-administered generic tool consists of a descriptive system with 5 questions in 5-point Likert-type format, which assess how significantly the domains of mobility, self-care, usual activities, pain/discomfort and anxiety/depression are affected in daily life. The EQ-5D-5L Index, based on health state valuations elicited from the general public ^{54,55}, is anchored at 0.0 (dead) and 1.0 (full health). A minimum increment of 0.03 in the EQ-5D-DL index score can be considered clinically important as it corresponds to the smallest coefficient for a change from 'No problem' to 'Some problems' within a dimension of the EQ-5D-DL. The EQ VAS asks individuals to rate their current state of health from "worst imaginable" to "best imaginable" on a 100-point scale. ⁵⁶ EQ-5D-5LTM is brief and has been extensively validated in various populations and disease states. Normative data for Canadians and ESKD exist. ^{11,57}

4.2.3 Secondary Outcomes

Participation in an exercise rehabilitation program may have additional benefits for patients that are not captured by the above outcomes. Therefore, the following secondary outcomes will be evaluated:

- 1. Change in time required for recovery following hemodialysis (in minutes) from baseline to 12, 26, and 52 weeks. At each study assessment, participants will be asked to answer the question "Approximately how much time does it take to recover from a dialysis session". Answers will be recorded in minutes. Prolonged post-HD recovery time, defined as the answer to the question "How long does it take to recover from a dialysis session" has recently been identified as a troubling symptom complex and important outcome unique to individuals receiving HD.^{58, 59}
- 2. Change in symptom burden from baseline to 26 and 52 weeks as measured by the Dialysis Symptom Index (DSI) Severity Score (Appendix B-1). This will be measured as the proportion of individuals who have a decline of 7 points or more in symptom burden as defined by DSI symptom severity score from baseline to 26 and 52 weeks. The DSI is a 30-item self-administered questionnaire with low administrative burden developed to measure the presence (yes/no) and severity ("how much did it bother you" by 5 point Likert-scale ranging from "not at all" to "very much") of common emotional and physical symptoms over the previous week in individuals receiving maintenance HD.⁵¹ Symptom severity scores can range from 0 to 150. A 7-point change in severity score is likely to be clinically significant because this magnitude of change is: a) consistent with the resolution/addition of 1 "very bothersome" symptom plus a 1 point change in severity of 2 symptoms and likely to be significant to patients; and b) is approximately 1 standard error of the mean based on our pilot data (SD 30, n=18) and consistent with distribution-based methods. The DSI has been shown to be reliable in predicting HRQOL in multiple studies in North American and European HD populations.^{6,51-53}
- 3. Change in physical activity behaviour patterns from baseline to 12, 26 and 52 weeks assessed:
- a. Using total active minutes per day as measured by multi-directional accelerometry. One week before each study assessment visit, participants will wear Actical Physical Activity MonitorsTM (Philips Respironics, Bend, OR) on their dominant hip during waking hours for a period of 7 days with 15 second epochs. This technique is considered the gold standard for physical activity assessment. ⁶⁰ During any cycling exercise, participants will wear the device on their dominant ankle. Valid files for analysis will require at least 3 days with a minimum of 8 h of wear time per day. Total active minutes will be calculated by summing the minutes per day spent in light intensity and moderate-to-vigorous physical activity (MVPA) based on pre-specified activity count cut points. ^{61, 62} Accelerometry is included to adjust for physical activity in the control group and address potential contamination.
- b. Using the Godin-Shephard Leisure-Time Exercise Questionnaire, which uses frequency and intensity of leisure time activity to calculate a total leisure time activity score. (REF)

The total leisure time activity score has been validated against measures of physical fitness and objective measures of physical level activity collected by accelerometry in individuals with chronic disease. ^{63, 64}

- **4.** Change in Exercise Capacity from baseline to 12, 26 and 52 weeks as measured by Incremental Shuttle Walk Test (ISWT) (Appendix B-3). Total distance is recorded as individuals walk 10-meter lengths to self-reported exhaustion at pre-programmed progressively increasing speeds as indicated by recorded beeps. ISWT has been used repeatedly in elderly and CKD populations, minimal clinically important differences have been established in chronic disease populations and results are correlated with other measures of exercise capacity. 65,66-68 ISWT was chosen to objectively measure physical function because standardized walking speeds at each stage make it less subject to measurement error due to variable participant effort than other similar tests.
- **5.** Change in frailty status from baseline to 12, 26 and 52 weeks assessed using the Modified Fried Criteria. ^{69,70} Defined as the presence of ≥ 3 criteria of the following criteria: weight loss; exhaustion; slowness; low physical activity; and weakness. As a predictor of adverse outcomes and associated with symptom burden, it is important to determine if frailty status can be modified through exercise
- **6.** Change in self-efficacy for exercise from baseline to 12, 26 and 52 weeks assessed using the Self-Efficacy for Exercise Survey (Appendix B-4). This self-reported tool consists of 9 brief questions in 10-point Likert scale format. The summary score indicates an individual's perception of their ability to successfully incorporate physical activity into daily routine and is the strongest determinant of continued exercise participation following formal exercise or rehabilitation programs. This measure has reliably predicted physical activity behavior in elderly individuals from various cultural backgrounds. The summary score indicates an individual score in the summary score indicates an individual's perception of their ability to successfully incorporate physical activity into daily routine and is the strongest determinant of continued exercise participation following formal exercise or rehabilitation programs. This measure has reliably predicted physical activity behavior in elderly individuals from various cultural backgrounds.
- **7.** Hospitalization rate defined as the number of hospitalization days admitted per patient year. In addition, cause and length of any hospital stay for greater than 24 hours will be collected. At each study assessment time point, this will be determined by self-report and hemodialysis chart review.
- **8.** All-cause mortality defined as the proportion of patients who die over 1-year and cause of death obtained from dialysis unit records. Depending on number of events, analysis may be adjusted for time on dialysis, age and comorbidities.

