7 STUDY SPECIFIC PROCEDURES

7.1 Study Procedures/Evaluations

The study-specific procedures and time-points to be done over the course of the study are summarized below and in Section 7.3 of the protocol:

Enrolled Study Population (both study groups)

- Informed Consent (enrolment, visit 0)
- Final study eligibility assessment including administration of DSI (enrolment, visit 0)
- Randomization (baseline)
- Collect Baseline Demographics age; gender; ethnicity/race (baseline, visit 1)
- Collect Past Medical History cause of end stage renal disease; diabetes; hypertension; smoking; cardiac disease/arrythmia; cerebrovascular disease/stroke/transient ischemic attack; lung disease; peripheral vascular disease/lower extremity amputation; arthritis; date of dialysis start; other relevant medical history (baseline, visit 1)
- Collect Concomitant Medications (each study visit)
- Collect vital signs/clinical data height, weight, BMI, systolic and diastolic blood pressure; dialysis adequacy (Kt/V); weekly intradialytic fluid gains; duration of HD and heart rate (each study visit; height will only be done on the 1st baseline visit)
- Collect Clinical Laboratory results (each study visit):
 - o Blood: hemoglobin, calcium, albumin, phosphate
- Patient compliance with the study protocol will be monitored in accordance to the Monitoring Plan (each study visit)
- Dialysis Symptom Index (enrolment visit and each study visit)
- EQ-5D-5L (each study visit)
- Time required for recovery following hemodialysis (each study visit)
- Download 7 day accelerometry history (each study visit)
- Godin-Shephard Leisure-Time Exercise Questionnaire (each study visit)
- Incremental Shuttle Walk Test (each study visit)
- Frailty status using the Modified Fried Criteria (each study visit)
- Self-Efficacy for Exercise Survey (each study visit)
- Cause and length of any hospitalization since last study visit (study visit 2, 3 and 4)
- Death (study visit 2, 3 and 4)

 Physical activity/exercise logs (collected weekly for first 12 weeks then every 2 weeks for next 40 weeks)

Intervention Group – Additional Evaluation

 Maximal incremental cycle test to volitional exhaustion⁷⁸ (After randomized to intervention and before intervention started)

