9.3.3 Secondary Outcomes and Analyses

We will repeat the primary outcome analyses that compared change in DSI from baseline to 12 weeks between groups, instead looking at change from baseline to 26 weeks and 52 weeks.

Change in EQVAS over time will be compared between study groups using Student's T-test. As well, we will compare the difference in proportion of individuals who develop new deficits (score of 2 or 3) in each domain of the EQ5D-5L over time. The degree to which change in symptom burden correlates with change in EQVAS will be assessed using Spearman and Pearson's correlation coefficients as indicated based on distribution of the data. Change in all other secondary outcomes over time will be compared between groups using the appropriate parametric and non-parametric statistical tests depending on data type and distribution. Bonferroni adjustments will be made for secondary outcomes to adjust for multiple study timepoints. Hospitalization will be analyzed using Poisson regression. For all analyses, two-sided p < 0.01 will be statistically significant. Statistical analysis will be performed using SAS 9.3 (Carey, NC).

We will validate the Godin Shepard Leisure-Time Exercise Questionnaire using accelerometry data. Correlation between Godin Questionnaire Score and active minutes (light, moderate and moderate-vigorous activity) measured by accelerometry at each study assessment time point will be assessed using Pearson or Spearman correlation depending on distribution of the data. Internal consistency of the Godin questionnaire will be assessed using Cronbach alpha and Intraclass Correlation Coefficient. In those individuals in which active minutes measured using accelerometry did not change between assessment periods (change of less than 10% from baseline), test re-test reliability of the Godin Questionnaire will be assessed using Kappa statistic. Responsiveness will be modelled using linear regression with Godin questionnaire score as the primary predictor of active minutes measured by accelerometry. Additional predictors including sex, age, diabetes and other comorbidities will be added to the model as sample size will allow.

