Appendix 3.5: Modified Fried Criteria

- (a) Unintentional weight loss of > 10 pounds in last year
- (b) Grip strength weakness (< 30 kg in males/< 20 kg in females (in strongest hand)
- (c) Exhaustion as determined by 2 questions from CES-D questionnaire
- (d) Slowness: established cut off for 4 metre timed walk adjusted for sex and height
- (e) Low physical activity: Godin-Shephard Leisure Time Index in lowest quintile of normative data stratified by age and sex.

[figure not shown]

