Appendix 4: Knowledge Translation Strategy

Appendix 5: COVID-19 Assessment Procedure

Renal Rehab Assessment COVID-19 Operating Procedure

- Participants only on intervention for 1 month will be approached to re-start the entire study again at HSC and SOGH (completed Mar 16, 2020)
- Controls continue
- No active participants currently at SBGH

Study Recruitment:

On hold until future

Activity Logs

 Will be collected by [name] and [name] (study kinesiologists) by phone or email following the timeline of the protocol

Baseline Assessments:

On hold until future

Assessments 2-4

- Questionnaires (DSI, Self Efficacy, EQ-5D-5L, Godin-Shephard Physical Activity) will be either:
 - Conducted over the phone ([name] or [name] will phone participants)
 - Emailed to participants to be filled out and emailed back (emailed by [name] or [name])
 - Mailed to participants with a postage-paid envelope for return to CDIC (mailed by [name] or [name])
- Recovery time, hospitalization since last assessment, exhaustion, and weight loss questions should still be asked

Accelerometers

- Will not be sent out via mail to participants to avoid potential transmission of COVID-19
- o Accelerometer data will not be collected at this time

• Participant Reimbursement

- When assessments are completed the participant will be mailed a \$25
 VISA/Mastercard gift card and a signature page with a postage-paid envelope for return
 - This envelope should be addressed to be returned to CDIC
- o [name] (research coordinator) will be mailing the gift cards out from home
- Participant addresses will be emailed to her over the secure WRHA email in a password protected document and deleted once letter addressed

- Signature pages will be collected in CDIC and given to [name] to compile and determine if a participant needs to be contacted again
- Physical Tests (Shuttle Walk, Gait Speed, Hand Grip Strength)
 - Unable to be completed at this time
- Clinical Outcomes Data Collection (chart reviews)
 - Chart reviews for assessments conducted after March 16th will be completed once research staff are able to return to work on dialysis units

Site Specific Procedure

Sherbrook Dialysis Unit ([name] still required to report to work for clinical component of his position as per Manitoba Renal Program)

- Call participant a week before scheduled assessment to select a time that works for them
- 2. Call participant day of assessment at chosen time and go over questions and questionnaires

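### Frailty is defined only as a yes/no status at 3 of 5 criteria and no analysis of the 0–5 count is pre-specified; under assumed inputs with several criteria responding, this gives up roughly 12 to 35 points of power

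*Combined protocol and SAP*

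**What the plan says.** - **Endpoint.** Section 4.2.3, item 5: "Change in frailty status from baseline to 12, 26 and 52 weeks assessed using the Modified Fried Criteria". The definition follows: "Defined as the presence of ≥ 3 criteria of the following criteria: weight loss; exhaustion; slowness; low physical activity; and weakness". The stated reason is that "it is important to determine if frailty status can be modified through exercise".
- **Collection.** Section 7.1 lists "Frailty status using the Modified Fried Criteria (each study visit"), and the schedule in 7.3 marks it at baseline, 12, 26 and 52 weeks. Appendix 3.5 lists five criteria, each scored yes or no, for example "Unintentional weight loss of > 10 pounds in last year" and "Grip strength weakness (< 30 kg in males/< 20 kg in females (in strongest hand"). A count from 0 to 5 can be derived wherever all five are measured.
- **Analysis.** Section 9.3.3 does not mention frailty by name. It falls under the general sentence: "Change in all other secondary outcomes over time will be compared between groups using the appropriate parametric and non-parametric statistical tests", with the choice left to data type and distribution. The same section sets two-sided p < 0.01 and Bonferroni adjustment over time points.
- **Exception.** Appendix 5 lists "Physical Tests (Shuttle Walk, Gait Speed, Hand Grip Strength") as not possible under the COVID-19 procedure. The exhaustion and weight-loss questions and the leisure-time exercise questionnaire continue.

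**The concern.** A cut at 3 of 5 discards most of the movement that an exercise programme might produce. Of the five possible one-criterion improvements (5→4, 4→3, 3→2, 2→1, 1→0), only 3→2 changes the status. Moves of 5→3 and 2→0 leave it unchanged, while 3→2 counts as much as 5→0.

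The plan treats its primary measure differently: section 9.3.1 analyses the symptom score both as a mean change and as a 7-point responder proportion. Frailty has no such pairing, and the documents cite no requirement that the arms be compared on the binary status. At stake is the power to answer the question that item 5 itself poses, in a trial whose sample size was set for a different endpoint.

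**Working it through.** **1. The plan's own figure.** Section 9.2 gives 58 per arm for 50% v 25% responders on the symptom score, 80% power, alpha 0.05:

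n = [1.960 × √(2 × 0.375 × 0.625) + 0.842 × √(0.50 × 0.50 + 0.25 × 0.75)]² / 0.25² = (1.342 + 0.557)² / 0.0625 ≈ 58.

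This reproduces, but it does not concern frailty, for which the documents state no power, prevalence, SD, correlation or effect. With 75 per arm and 30% dropout, 75 × 0.70 = 52.5, so 52 per arm are taken as evaluable.

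**2. Cost of a cut, analytically.** If the count is treated as roughly normal, dichotomising at prevalence p keeps a fraction φ(c)² / [p(1 − p)] of the information, where c is the cut-point. Power for status is Φ[(z₁₋α/₂ + z_power) × √fraction − z₁₋α/₂]. For p = 0.4 and 80% power on the count at 0.05: (1.960 + 0.842) × √0.622 − 1.960 = 0.25, so 60%.

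| Proportion frail (assumed) | Information kept | Status power at 0.05 | at 0.01 | at 0.01/3 |
|---|---|---|---|---|
| 20% | 0.490 | 50% | 43% | 39% |
| 30% | 0.576 | 57% | 51% | 47% |
| 40% | 0.622 | 60% | 55% | 52% |
| 50% | 0.637 | 61% | 56% | 53% |

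Each row takes 80% power for the count at the same alpha. Over count power of 50–90%, the loss is 15–30 points at 0.05, 20–37 at 0.01 and 22–41 at 0.01/3.

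**3. Simulation of five correlated yes/no criteria at two visits.** All frailty inputs are assumed. Gain of the adjusted count over adjusted status at 0.05:

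- 52 per arm, 25–60% frail, correlation 0.35 between criteria and 0.5–0.7 between visits: 12–33 points.
- 52, 58 or 75 per arm, about 23–50% frail, count SD 1.3–1.7, visit correlation 0.36–0.69: 14–34 points.
- 52 per arm, three or more criteria responding: 16–29 points.

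Worked example: 52 per arm, 36% v 22% frail at follow-up, count difference 0.54. Power is 35% for chi-square on status, 40% for adjusted status and 67% for the adjusted count. The like-for-like gain is 67 − 40 = 27 points. Against the chi-square it is 67 − 35 = 32, of which 40 − 35 = 5 comes from baseline adjustment rather than from the count.

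**4. Where the gain is smaller.**

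- Follow-up only, no baseline: 6–22 points at 52 per arm; 7–27 in the series that also includes 58 and 75 per arm.
- Unadjusted change in count against follow-up status: as low as 2 points in the least favourable scenario.
- One responding criterion: about 2–3 points adjusted; 3–10 in a run where only the activity criterion shifted.

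**5. At the threshold in 9.3.3.** If Bonferroni is applied to 0.01 over three time points, alpha is 0.01/3 = 0.0033. For status, 36% v 22% with 52 per arm: SE = √[(0.36 × 0.64 + 0.22 × 0.78)/52] = 0.088 and 0.14/0.088 ≈ 1.59. Power is Φ(1.59 − 1.96) ≈ 36% at 0.05, Φ(1.59 − 2.58) ≈ 16% at 0.01 and Φ(1.59 − 2.94) ≈ 9% at 0.0033.

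For the adjusted count (45% frail, 20-point status difference, correlations 0.35 and 0.6, 52 per arm), power is 83%, 62% and 46% at the same three levels. Adjusted status in that scenario has 38% at 0.01, a gap of 62 − 38 = 24 points.

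**6. COVID-affected visits.** Three criteria remain. If k of them are met, the true count lies between k and k + 2. Status is known for k = 3 (frail) and k = 0 (at most 2, not frail), and unknown for k = 1 or 2. The full count is never known.

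**The case against.** The strongest case for the plan has four parts.

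- **Status is what the trial asks about.** Item 5 speaks of frailty status because it predicts adverse outcomes. This stands, and it is why the proportion frail should stay in the report. It does not explain why the count should go unanalysed.
- **A reader might infer that frailty will be tested only as yes/no.** The text does not go that far. Section 9.3.3 names no frailty test, and the synopsis lists linear mixed modelling as a possibility for secondary outcomes. What can be said is that the only defined endpoint is binary and no count analysis is pre-specified.
- **The count is not always available.** A reader might take the visit schedule to mean that the 0–5 count exists at every visit. Under Appendix 5 it does not, and status survives there for some patients when the count does not. The number of such visits is not given. This stands, and the fix needs a rule for it.
- **The gain depends on how exercise acts.** The activity criterion in Appendix 3.5 is scored from the leisure-time exercise questionnaire, which taking part may itself raise. If that criterion alone moved, the count would gain little and the shift would be hard to interpret. This also stands.

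The general statement on data type does not meet the point: with the outcome defined as a status, the natural reading is a categorical comparison.

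**Conclusion.** The point holds as a low-severity improvement to a secondary outcome for which the plan claims no power. If several criteria respond, with 52 per arm and 25–60% frail, the baseline-adjusted count gains roughly 12 to 35 points over baseline-adjusted status at two-sided 0.05. Without baseline adjustment or with one responding criterion, it gains about 2 to 22 points, although one unadjusted series that included larger arms reached 27.

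Three stronger readings are not supported. No single figure for lost power can be derived from the documents, because they contain no frailty inputs. The count would not make frailty well powered under the plan's own threshold: 83% at 0.05 became 46% at 0.01/3 in the scenario above. And nothing says that a null frailty result would be carried into a later trial: section 2.1.4 speaks only of gathering information for a multicentre trial with frailty among its outcomes.

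**What to change.** In section 9.3.3:

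1. Pre-specify an ordinal or linear model for the number of Modified Fried criteria (0–5) at each visit, adjusted for the baseline count.
2. Report the proportion with 3 or more criteria by arm beside it. Showing each criterion by arm would also reveal whether a shift comes from the activity criterion alone.
3. State how visits without gait speed and grip are handled, for example as missing under the plan's multiple imputation. Sections 9.3.1 and 9.3.4 start imputation only when missing outcomes exceed 25%, so say whether that trigger applies to frailty.
4. State the alpha for this comparison, including how p < 0.01 and the Bonferroni adjustment combine.

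The cost is SAP wording: no new visits, measurements or participants. The downsides are that the effect becomes a shift in number of criteria, which needs the proportion frail beside it, and that the five-item count cannot be formed at COVID-affected visits.
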